Study Proposal & Statistical Analysis Plan

**Phase I/IIa Study of Pharmacokinetics and Safety of Atorvastatin in
Children with Coronary Artery Abnormalities Secondary to Kawasaki
Disease**

Investigators:

**[name], MAS
[name]**

May 20, 2016

NCT# 01431105

I. Study Overview

OVERALL OBJECTIVE

The goal of this study is to determine the safety, pharmacokinetics and activity of atorvastatin in children with acute Kawasaki disease (KD) and coronary artery abnormalities. The goal will be to find a treatment that could prevent or attenuate coronary artery damage in acute KD.

HYPOTHESIS

We postulate that atorvastatin will be safe in children ≥ 2 years old with acute KD.

STUDY TYPE

This is a Phase I/IIa dose escalation study

STUDY POPULATION

Children ≥ 2 years to 17 years with acute KD who have a Z-score ≥ 2.5 or aneurysm (≥ 1.5 x the adjacent segment) of one of the coronary arteries.

STUDY DURATION

4 years

PRIMARY OUTCOME

Safety of atorvastatin in the study population.

SECONDARY OUTCOMES

1. Pharmacokinetics of atorvastatin
2. Activity of atorvastatin
 - a. Biomarkers and measures of inflammation
 - b. Echocardiographic assessment of coronary artery abnormalities

II. Background & Significance

IIA. Significance:

KD, the most common cause of acquired heart disease in children in Western developed countries and Asia, is a systemic vasculitis of unknown etiology. In the United States, there are 5-6,000 new cases each year [1]. However, without a specific diagnostic test, the true burden of disease is unknown. At Rady Children's Hospital San Diego, we cared for over 90 new KD cases in 2010 and follow over 1,200 families in our outpatient KD Clinic (350 outpatient visits/yr.), of whom 9% developed aneurysms and 25% developed dilated coronary arteries. In Japan, the country of highest incidence ($>215/100,000$ children < 5 yrs), there are more than 12,000 new cases each year and rates continue to rise [2]. KD causes both a myocarditis and a vasculitis that damages the coronary arteries and other medium-sized muscular arteries [3, 4]. The major sequelae of aneurysms include thrombosis, late coronary artery stenosis, myocardial ischemia, myocardial infarction, and death [5, 6]. **Clearly, aneurysm prevention is a primary goal of treatment during the acute phase of the disease, which leads us to focus on treatment of patients with early signs of coronary artery abnormalities (CAAs) in this application.**

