6. Males engaging in sexual activity that could lead to pregnancy must use a condom.

VB. Exclusion Criteria:

1. Use of a statin, fibrate, or niacin within the 3 months prior to enrollment
2. Have any chronic disease, except asthma, atopic dermatitis, autism or controlled seizure disorder
3. Screening creatine phosphokinase (CK) \geq 3x upper limit of normal for age
4. Patient taking a CYP3A4 inhibitor (i.e. cyclosporine, clarithromycin or doxycycline) in the last 7 days
5. Patient has a history of allergy to atorvastatin or its derivatives

VC. Data Collection: The following data will be recorded for all patients:

1. Demographic data:

- Patient's age at KD onset, sex, self-reported ethnicity of each biologic parent

2. Clinical data:

- Physical findings confirming the KD case definition (**Table 2**)[10]
- Illness day at study entry
- Response to IVIG (IVIG-resistance will be defined as persistent or recrudescing fever ($T \geq 38.0^{\circ}\text{C}$ rectally) \geq 36 h and $<$ 7d following the end of the IVIG infusion (2g/kg)[14].) -
- Name, dose and indication of concomitant medications taken from enrollment until study completed
- Complete blood count, C-reactive protein (CRP), high sensitivity CRP (hsCRP), erythrocyte sedimentation (ESR), aspartate aminotransferase (AST), ALT, and GGT at baseline, 2 weeks and 6 weeks
- CK and fasting lipid panel at baseline (after enrollment), 2 weeks and 6 weeks

VI. Statistical analyses

Incidence rates of adverse events and the proportion of subjects prematurely withdrawn from the study due to adverse events was compiled. For continuous variables, the Kruskal Wallis Test was performed to compare the four dose levels. For categorical variables, Fisher's Exact Test was performed. Statistical analyses were performed using the statistical software R (version 3.4.4) (<http://www.r-project.org>). Analyses were performed following the intent-to-treat principle. No adjustments for multiple comparisons were made for secondary analyses, and a p-value of 0.05 was considered statistically significant.

VII. Literature Cited

1. Kaneko, K., et al., *Prediction of the Risk of Coronary Arterial Lesions in Kawasaki Disease by Brain Natriuretic Peptide*. *Pediatr Cardiol*.
2. Nakamura, Y., et al., *Epidemiologic Features of Kawasaki Disease in Japan: Results of the 2007-2008 Nationwide Survey*. *J Epidemiol*, 2010.

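### Section VI gives no reference distribution for the four-group Kruskal-Wallis test; if chi-square is used and dose cohorts are small, the test is conservative, and a permutation p-value is a cheap improvement

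*Combined protocol and SAP*

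**What the plan says.** The Study Type paragraph of Section I states: "This is a Phase I/IIa dose escalation study". Section VI (Statistical analyses) sets out the comparisons between doses:

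- Continuous data: "For continuous variables, the Kruskal Wallis Test was performed to compare the four dose levels".
- Categorical data: "For categorical variables, Fisher's Exact Test was performed".
- Software: "Statistical analyses were performed using the statistical software R (version 3.4.4"). No function and no exact or permutation option is named.
- Threshold: "a p-value of 0.05 was considered statistically significant".
- Multiplicity: "No adjustments for multiple comparisons were made for secondary analyses".

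For safety, the primary outcome, the same section says: "Incidence rates of adverse events and the proportion of subjects prematurely withdrawn from the study due to adverse events was compiled". No Kruskal-Wallis decision rule is attached to that summary.

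The documents give no cohort size, total sample size, effect size or power. They do not list which continuous variables are tested. Section VC shows what is collected at baseline, 2 weeks and 6 weeks: blood count, CRP, hsCRP, ESR, AST, ALT, GGT, CK and fasting lipids.

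**The concern.** The Kruskal-Wallis statistic H can be referred to a chi-square distribution with 3 degrees of freedom (four groups) or to its own permutation distribution. The two agree in large groups. In small groups the chi-square tail is too heavy near the 5% point, so the p-value comes out too large and the test rejects less often than its nominal level.

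Section VI leaves the choice open for continuous data, while the test it names for categorical data is exact. A dose-escalation study may well have small dose levels. Kruskal-Wallis is the only between-dose comparison the plan offers for continuous measures such as CK, liver enzymes and inflammatory markers. A p-value that leans towards no difference would slightly weaken what the trial can say about dose and laboratory safety, or about dose and anti-inflammatory activity.

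**Working it through.** **Inputs from the documents.** Four dose levels, so 3 degrees of freedom; threshold 0.05; no reference distribution. All are from Section VI. The plan states no sample size or power, so there is no design figure to reproduce.

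**Assumed inputs.** Chi-square reference; cohort sizes from 2 to 12 per level plus some unequal splits; no ties; normal data with means at 0, 0.5, 1.0 and 1.5 SD for the power figures.

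**Formula.** H = 12 / (N(N+1)) × Σ(Rⱼ² / nⱼ) − 3(N+1), where Rⱼ is the rank sum and nⱼ the size of level j, and N is the total. The chi-square rule rejects when H ≥ 7.815. The exact rule rejects when H reaches the smallest value whose permutation tail probability is at most 0.05.

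**Hand check, 2 per level.** The most extreme rank sums are 3, 7, 11 and 15. Σ(R²/n) = (9 + 49 + 121 + 225)/2 = 202, so H = (12/72) × 202 − 27 = 6.667. This is below 7.815 (chi-square p = 0.083). With 2 per level the chi-square test can never reach 0.05.

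**Hand check, 3 per level, doses completely separated.** The rank sums are 6, 15, 24 and 33. Σ(R²/n) = (36 + 225 + 576 + 1,089)/3 = 642, so H = (12/156) × 642 − 39 = 10.385. Chi-square p = 0.0156. The exact p is 24/369,600 = 0.000065, because 24 orderings of the four levels give this H out of 369,600 equally likely arrangements. This is the extreme case, not a typical one.

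**Level and power.** The null distribution for 3 per level was fully enumerated. Larger layouts used 800,000 random permutations, and power used 100,000 simulated trials per layout.

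| Children per level | Exact 5% cut-off for H | Chi-square p at that cut-off | True level, chi-square rule | Power, chi-square | Power, exact | Loss (points) |
|---|---|---|---|---|---|---|
| 3 | 7.000 | 0.072 | 2.05% | 10.6% | 18.7% | 8.1 |
| 4 | 7.235 | 0.065 | 3.4% | 24.7% | 31.1% | 6.4 |
| 6 | 7.440 | 0.059 | 4.0% | 46.5% | 50.6% | 4.1 |
| 8 | 7.551 | 0.056 | 4.35% | 64.5% | 66.9% | 2.4 |
| 10 | 7.595 | 0.055 | 4.5% | 77.4% | 78.9% | 1.5 |
| 12 | 7.632 | 0.054 | 4.6% | 86.3% | 87.2% | 0.9 |

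At 3 per level the permutation distribution is coarse. The strict cut-off 7.000 has a tail probability of 4.4%. The next value down, 6.897, has 5.02% and gives about 21% power. That is why the loss there is put at 8 to 10 points.

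**Unequal cohorts.** The true level of the chi-square rule is 3.25% for 3/3/3/20, 3.9% for 3/6/6/19 and 4.3% for 6/6/6/16. A few small levels are enough to make the test conservative even when one level is large.

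**Direction.** In all 13 layouts tried, every chi-square p-value in the exact range 0.01 to 0.10 was larger than the exact one.

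**The case against.** The strongest reply is that both premises lie outside the documents. Section VI does not say that chi-square was used, and silence is not use. No cohort size is stated either. A Phase I/IIa study meant to inform a decision on Phase III could have had 10 or more children per level, and then the loss is 2 points or less. This stands: the point is conditional on both assumptions.

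A reader might infer that the plan's p-values fail to keep their stated 5% error rate, or that real dose differences are being missed because of the test. The documents do not support either reading. A conservative test stays within 5%. At 3 per level the exact test also has only about 19% power against a 1.5 SD spread, so it misses about 81% of such differences. The shortage of children, not the reference distribution, accounts for most of that. Much larger power gaps appear if the assumed spread is 2.25 to 3 SD across the doses with cohorts of 3, but nothing in the plan points to effects of that size.

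A reader might also infer that the primary safety conclusion is compromised. It is not: adverse-event incidence and withdrawals are compiled without this test, and no escalation or decision rule refers to it.

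The contrast with Fisher's test is weak, since exactness is part of that test's name and does not establish a policy of exact inference.

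What survives is that a permutation p-value is valid at any cohort size, so the recommendation does not depend on which assumption turns out to be true.

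**Conclusion.** The point holds in conditional form, as a cheap improvement and not as an error in the plan. Section VI leaves both the reference distribution and the cohort sizes unstated. Under a chi-square reference and about 3 to 6 children at some or all levels, the effect is material at about 2 to 5 per level, modest at 6 to 8, and negligible from 10 upwards. An exact p of about 0.044 at 3 per level would be reported as 0.072. At 6 per level a result on the exact 5% boundary would be reported as 0.059. The figures assume no ties and normally distributed data with evenly spaced dose effects; other patterns change the power losses by a few points (at 3 per level, roughly 8 to 12 over the three patterns tried).

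**What to change.** Add one sentence to Section VI: Kruskal-Wallis p-values are taken from the exact or Monte Carlo permutation distribution (at least 100,000 permutations, ties kept), not from the chi-square approximation. State the number of children analysed at each dose level beside it, so that the reader can judge how much the choice matters.

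The cost is one sentence and about one line of code, with no new data. There is one downside to disclose. The per-test false-positive rate rises from about 2 to 4% to about the stated 5%, and secondary analyses carry no multiplicity adjustment. As an illustration, seven markers (CRP, hsCRP, ESR, AST, ALT, GGT, CK) at three visits would be 7 × 3 = 21 tests, if all were run. With 3 children per level, expected false positives would rise from 21 × 0.0205 = 0.43 to at most 21 × 0.05 = 1.05. That is the rate the plan already accepts, but these p-values should be read as exploratory.

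### Section VI's only method for continuous data, an omnibus Kruskal-Wallis test across dose levels, would give no pharmacokinetic estimate, although PK is the first secondary outcome

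*Combined protocol and SAP*

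**What the plan says.** The title and the overall objective in Section I both name pharmacokinetics, and the first secondary outcome is "Pharmacokinetics of atorvastatin". Section VI has one sentence for continuous data, with no exception: "For continuous variables, the Kruskal Wallis Test was performed to compare the four dose levels". The other stated rules are "For categorical variables, Fisher's Exact Test was performed", a threshold under which "a p-value of 0.05 was considered statistically significant", and "Analyses were performed following the intent-to-treat principle".

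Section VI does not mention PK. No section names a PK parameter, a sampling time, a way of deriving parameters or a PK-evaluable set. The data list in Section VC covers blood count, inflammatory markers, liver enzymes, CK and lipids. It includes neither drug concentration nor body weight. It does include "Name, dose and indication of concomitant medications taken from enrollment until study completed". Exclusion criterion 4 covers CYP3A4 inhibitors in the 7 days before entry.

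**The concern.** AUC, Cmax and clearance are continuous, so read literally the Section VI rule covers them, and the documents offer nothing else. For raw exposure, the null hypothesis is that children given four different doses have the same exposure. That is false by design. Rejecting it does not show whether exposure rises in proportion to dose, and failing to reject it in small cohorts could be misread as no dose effect.

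A dose-escalation PK study in children aged 2 to 17 needs to know how exposure rises with dose and how much it varies between children. A p-value supplies neither, so a later trial would have no estimate or interval from this analysis to support its choice of dose.

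**Working it through.** **The plan's own figure.** There is none to reproduce. The documents state no sample size, power or PK precision.

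**Inputs.** From Section VI: four dose levels, a Kruskal-Wallis test and a 0.05 threshold. Everything else is assumed: log-normal exposure; dose ratios from 1:2:3:4 to 1:2:4:8; 3 to 10 children per level; between-child CV 40% to 100%; mean exposure proportional to dose^b. The value b = 1 is exact proportionality. For scale, b = 1.5 means that dose-normalised exposure at the top dose is 4^0.5 = 2.0 times that at the bottom dose over a 4-fold range, and 8^0.5 = 2.8 times over an 8-fold range.

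**What each version tests.** On raw exposure, the null is b = 0. On dose-normalised exposure, or on apparent clearance (dose/AUC, which reverses the same ranks), the null is equal values at every dose, which is b = 1. The power model is ln(exposure) = a + b·ln(dose), with b compared with 1.

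**Simulation 1.** 6 or 10 per level; CV 50% or 80%; ratios 1:2:3:4, 1:2:4:6 and 1:2:4:8; 4,000 trials per setting.

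| Analysis | b = 1.0 | b = 1.5 |
|---|---|---|
| Kruskal-Wallis, raw exposure, rejects at 5% | 73-100% | 98-100% |
| Kruskal-Wallis, dose-normalised or clearance, rejects at 5% | 4-5% | about 21-99% |
| Power-model slope test, rejects b = 1 at 5% | 5% (nominal) | 42-100% |
| Power-model 90% CI excludes 1 | 9-11% | 54-100% |

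The fair comparison of power is between the second and third rows, both at 5%. The last row works at a 10% error level. The 90% CI half-width for b is about 0.16 to 0.47.

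**Simulation 2.** Smaller departures from proportionality, 1,500 trials per setting. Example with 6 per level, CV 70%, ratio 1:2:4:8:

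| Analysis (5% level) | b = 0.7 | b = 1.0 | b = 1.3 |
|---|---|---|---|
| Kruskal-Wallis, raw exposure | 85% | 100% | 100% |
| Kruskal-Wallis, dose-normalised | 21% | 4% | 22% |
| Power-model slope test | 41% | 5% | 42% |

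**Precision in the same example.**
- σ = √ln(1 + 0.7²) = 0.631.
- The log doses 0, 0.693, 1.386 and 2.079 have squared deviations summing to 2.402. With 6 children each, Sxx = 14.41.
- The 90% half-width for b is t(0.95; 22)·σ/√Sxx = 1.717 × 0.631/3.797 = 0.29. Over the 8-fold range this is a factor of 8^0.29 = 1.83 either way on the top-to-bottom ratio of dose-normalised exposure.
- The 95% CI factor for geometric-mean clearance over all 24 children is exp(2.069 × 0.631/√24) = 1.31.

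**Very small cohorts.** With 3 per level and ratio 1:2:3:4, raw-exposure Kruskal-Wallis under exact proportionality rejects in 64%, 24% and 14% of trials at CV 40%, 70% and 100%. A value of about 17% falls within that range. Against b = 0.7 or 1.3, over both ratios and all three CVs, dose-normalised Kruskal-Wallis has 3-13% power and the slope test 8-47%. The 90% half-width for b reaches 0.84 at worst.

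**The case against.** The strongest reply is that Section VI never says its rule applies to PK. The variables listed in Section VC are laboratory measures, for which a comparison of dose levels is sensible. A general sentence plus silence on PK is then a gap, not a chosen PK method. This stands as a reading of intent. It does not remove the need to edit: either the rule covers PK and suits it poorly, or PK has no stated analysis.

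A second reply is that Kruskal-Wallis is not worthless for PK. This also stands. On clearance or dose-normalised exposure it keeps its error rate (about 2% to 5.5% over the settings of the second simulation) and can detect non-proportionality. A reader might infer from the raw-exposure figures that the test is uninformative, but that holds only if exposure is left undivided by dose, and the plan does not say which form would be used.

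A reader might also infer that the PK outcome cannot be answered at all. The documents do not support that. Section numbers run from II to IV, so the file may be abridged, and a separate PK plan cannot be excluded.

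Finally, replacing the test does not supply missing parameters or sampling times. That is right. The change proposed here concerns how PK results are analysed once they exist.

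**Conclusion.** The point holds in a limited form. The one stated method for continuous data gives no PK estimate or interval and ignores dose order. On raw exposure a significant result hardly separates proportional from strongly non-proportional PK at 6 to 10 per level. On dose-normalised exposure it is valid, but in the worked example it has about half the power of a slope test at the same error level (21-22% against 41-42%).

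Every percentage depends on assumed dose ratios, cohort sizes and CVs. At 3 per level the raw-exposure test can often fail to reject even when exposure is exactly proportional, so the risk there is a false reading of no dose effect. The conclusion that no estimate is produced does not depend on these assumptions. This is a change that should be made, held with medium confidence because a PK plan may exist outside this file.

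**What to change.** In Section VI, state that Kruskal-Wallis is not the analysis of PK exposure. Then, for the PK parameters derived from the samples the trial takes:

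1. Name the parameters, and report the geometric mean, CV% and confidence interval at each dose level.
2. Fit ln(exposure) = a + b·ln(dose given), and report b with its 90% CI against 1.
3. Plot apparent clearance against age, and against weight only if weight is recorded; Section VC does not list it.
4. As a sensitivity summary, leave out PK samples taken while a CYP3A4 inhibitor is logged as a concomitant drug. This needs start and stop dates, which Section VC does not name.

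If a separate PK plan exists, cite it in Section VI and exempt PK from the Kruskal-Wallis rule.

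The analysis change costs some wording and a short regression. Whether it needs further data cannot be judged from these documents, because they describe no PK sampling. The downside is the log-linear assumption, which a plot of dose-normalised exposure against dose will check. With small cohorts the interval for b may be wide, and it should be reported as such.

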Barriers to improving treatment for children with KD include the lack of a validated predictive score to identify those children at highest risk of aneurysm formation and lack of a therapeutic intervention that can prevent progression of CAAs once they have been detected.

IIE. Potential to effect change in clinical practice

The current clinical practice is to give every patient the same standard therapy (IVIg 2g/kg with aspirin 80-100mg/kg) and to monitor for CAA. The mechanism of action of this immunomodulatory therapy remains unknown, but is being addressed by other research by the PI in collaboration with [name] (RO1 HL103536 and RO1 FD003514). In the unfortunate child who carries the genetic risk for CAA, no intervention to modify vessel wall inflammation is currently recommended [10].

In a recent article entitled “Mining for therapeutic gold”, Director of the NIH, [name], stated that “drug repurposing” should be a strategy “to translate research into clinically useful products” [11]. Our goal is to translate our findings on the role of matrix metalloproteinases (MMPs), T-cells, and myofibroblasts in KD aneurysm formation and “repurpose” the drug atorvastatin to test the hypothesis that the pleiotropic anti-inflammatory properties of this drug will prevent or attenuate coronary artery aneurysms in children with KD.

IV. Specific Aims

Specific Aim 1 will test the hypothesis that a 6-week course of atorvastatin will be safe and well-tolerated in children with KD and early CAAs.

The safety of atorvastatin will be assessed. A dose escalation design will be used to find a dose in subjects that is tolerated with limited side effects.

V. Human subjects

VA. Inclusion criteria:

1. Age \geq 2 years to 17 years old
2. Meets clinical criteria for KD according to AHA guidelines (Table 2): Fever ($T \geq 38.0^{\circ}\text{C}$ or 100.4°C by oral or rectal route; if measured by a non-core route (i.e. Axillary, ear, temporal artery), then add 0.5°C to temperature; by history acceptable) \geq 3 days and \geq 2 clinical criteria with LAD/RCA z-score \geq 2.5 or an aneurysm (\geq 1.5 x the adjacent segment) of one of the coronary arteries
3. Patient presents within the first 20 days after fever onset
4. Parent or legal guardian able and willing to provide informed consent and subject willing and able to provide assent when appropriate.
5. Post-menarchal females: Negative pregnancy test at screening and willing to use two forms of contraception during the study

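### The only analysis-population rule is an unqualified intent-to-treat sentence, so the primary safety rates have no treated denominator and no stated dose grouping

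*Combined protocol and SAP*

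**What the plan says.** Section I (Study Overview) describes the design as follows: "This is a Phase I/IIa dose escalation study". The primary outcome is "Safety of atorvastatin in the study population", and the first secondary outcome is "Pharmacokinetics of atorvastatin". Section IV (Specific Aims) gives the purpose of escalating: "A dose escalation design will be used to find a dose in subjects that is tolerated with limited side effects".

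Section VI holds the analysis rules. For safety: "Incidence rates of adverse events and the proportion of subjects prematurely withdrawn from the study due to adverse events was compiled". For comparisons between levels: "For continuous variables, the Kruskal Wallis Test was performed to compare the four dose levels", with Fisher's exact test for categorical variables. The one statement about who is analysed is "Analyses were performed following the intent-to-treat principle".

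The supplied text names no safety, treated or dose-received set. It does not give the denominator for AE incidence. It does not say whether the four levels are groups by dose assigned or by dose received.

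**The concern.** Intent-to-treat exists to protect a randomised comparison, and none is described here. The study has to show how well each dose is tolerated, and that can be read only from children who took the dose. Taken in its ordinary sense, the rule does two unhelpful things to the primary analysis.

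1. A child enrolled but never dosed stays in the AE denominator. This can only lower a treatment-emergent rate. An all-AE rate could move either way, since an undosed child with acute Kawasaki disease may still have an event.
2. A child who took a level other than the one assigned is counted at the assigned level. This can bias a comparison between levels in either direction.

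What is at stake is which children, at which dose, the primary safety rate describes. If cohorts are small, one child is enough to move a rate by several percentage points.

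**Working it through.** The documents give no cohort size, AE count, or count of undosed or off-dose children, so there is no stated figure to reproduce. All inputs below are assumptions chosen to show scale. Intervals are exact (Clopper-Pearson) 95%, and Fisher tests are two-sided.

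**Undosed children.** Let m children be dosed, x of them with an AE, and let u be enrolled but undosed, y of them with an AE. The treated rate is x/m and the intent-to-treat rate is (x + y)/(m + u). The second is lower when y/u < x/m and higher when y/u > x/m.

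| Assumed case | Treated | Intent-to-treat | Shift (points) |
|---|---|---|---|
| 6 dosed, 2 AEs; 1 undosed, no AE | 2/6 = 33.3% (4.3 to 77.7) | 2/7 = 28.6% (3.7 to 71.0) | -4.8 |
| 6 dosed, 2 AEs; 1 undosed, with AE | 2/6 = 33.3% | 3/7 = 42.9% (9.9 to 81.6) | +9.5 |
| 6 dosed, 2 AEs; 2 undosed, no AE | 2/6 = 33.3% | 2/8 = 25.0% | -8.3 |
| 12 dosed, 2 AEs; 1 undosed, no AE | 2/12 = 16.7% | 2/13 = 15.4% | -1.3 |
| 12 dosed, 2 AEs; 1 undosed, with AE | 2/12 = 16.7% | 3/13 = 23.1% | +6.4 |

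**Off-dose children.** Assume two levels of 6, with 3 AEs at the higher and 1 at the lower as assigned. One child assigned the higher level took the lower. Each of the 12 children is in one group only.

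| Grouping | Higher level | Lower level | Difference (points) | Fisher p |
|---|---|---|---|---|
| As assigned | 3/6 = 50.0% | 1/6 = 16.7% | 33.3 | 0.545 |
| As received, moved child had no AE | 3/5 = 60.0% | 1/7 = 14.3% | 45.7 | 0.222 |
| As received, moved child had an AE | 2/5 = 40.0% | 2/7 = 28.6% | 11.4 | 1.000 |

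The intervals are wide and overlap, and no Fisher result approaches 0.05. The illustration shows that the choice of set changes the reported rate. It does not show that a test result would change.

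**Could a child be enrolled but undosed?** Section VC (Data Collection) lists "CK and fasting lipid panel at baseline (after enrollment), 2 weeks and 6 weeks". Enrolment therefore comes before at least one baseline step, which leaves room for a child to leave before dosing. The line fixes when blood is drawn. It does not give the time of the first dose and is not evidence that anyone left.

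**The case against.** The strongest reply is that the sentence may mean something harmless. With no randomisation described, and with withdrawals for AEs reported in the same section, it may mean only that no child is dropped for stopping early. On that reading it protects the safety analysis by keeping children who stopped because of toxicity. This stands as a possible reading, and any replacement must keep that protection. But the sentence as written does not choose between the readings, and even the benign one leaves the AE denominator and the dose grouping unstated.

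It can also be said that every number above is assumed and that the effect may be zero. Both are true. They limit the claim to a mismatched and ambiguous rule, with no demonstrated bias.

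A reader might infer three stronger things:

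- *That undosed children distort the pharmacokinetic results.* The documents do not support this. Section VI describes no pharmacokinetic method, and an undosed child has no drug exposure to summarise. Only an off-dose child could be misplaced in a by-dose pharmacokinetic summary.
- *That the reported safety rates are in fact diluted or misgrouped.* No undosed or off-dose child is documented.
- *That regrouping will always change the picture for off-dose children.* It depends on the rule. Grouping by first dose level taken differs from assigned-dose grouping only when the first dose was at the wrong level.

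Finally, the section numbering runs from II to IV, so a section may be absent from the supplied text. The finding rests on the text supplied. Section VI is nevertheless the analysis section, and its rule carries no exception.

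**Conclusion.** The concern holds in limited form, as something that should be fixed. One unqualified intent-to-treat rule is poorly matched to a dose-escalation study with safety as the primary outcome and no randomisation described. In its ordinary sense it counts undosed children and groups by assigned dose, whereas the study's purpose calls for a treated set grouped by dose received.

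The size is unknown from the documents, and zero if every enrolled child took the assigned dose. Under the assumptions shown, one undosed child shifts a level's AE rate by between -4.8 and +9.5 points with 6 dosed, and between -1.3 and +6.4 points with 12 dosed. One off-dose child changes a 33.3-point difference between levels to 45.7 or 11.4 points. For pharmacokinetics, the point extends only to dose grouping in any by-dose summary, and that is an inference from the general rule.

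**What to change.** For the primary safety analysis, replace the sentence with a definition along these lines:

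- **Safety set:** all children who took at least one dose of atorvastatin, including those who stopped early or withdrew.
- **Grouping:** each child counted once, by dose level actually received, under one stated rule. One group per child keeps the groups independent for Fisher's exact and Kruskal-Wallis tests. First dose level taken is one possible rule; if it is used, state its limit for children whose dose changed later.
- **Dose changes:** list events after any dose change descriptively, with the dose at onset.
- **Counts:** report the number of undosed and off-dose children at each level, including zero, so that a reader can see whether the choice of set matters.
- **Other outcomes:** keep assigned-dose grouping for the activity outcomes and say so. Base any by-dose pharmacokinetic summary on the dose actually taken.

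The cost is one paragraph of wording and minor re-tabulation, since Section VI describes the analyses as already done. AE rates may look slightly less favourable if undosed children without events leave the denominator. If every child was dosed as assigned, no result changes.
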